### 7.4.3 30- and 60-Day All-cause Mortality

The percentage of 30- and 60-day all-cause mortality will be calculated based on each subject's date of death relative to C1D1 (ie, date of death minus date of C1D1). Subjects who died within 30 days will also be included in the 60-day mortality calculations. To avoid using a different denominator for calculation of the percentage of 30- and 60-day mortality, subjects who were lost-to-follow-up within 30- or 60-days from C1D1 (assumed to be a very small number, if any) will be considered alive for the corresponding 30- and 60-day mortality calculations. Causes of death and relationship to study treatment will also be summarized.

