Safety as assessed by early 30- and 60-day all-cause mortality rates, as well as Grade ≥ 3 toxicities, are comparable to those of TC therapies except for a higher incidence of febrile neutropenia on SGI-110 (Table 10).

Table 10: SGI-110 Safety Compared with Other Therapies for Previously Untreated Elderly Subjects with AML

Common Grade ≥ 3 AEs and All-Cause Mortality	% Subjects				
	Phase 2	Kantarjian, Thomas et al. 2012	LDAC	Dombret et al 2014	Burnett et al 2007
	SGI-110 (N=51)	Decitabine IV (N=238) ^a	LDAC (N=208) ^a	Azacitidine (N=241)	LDAC (N=102) ^a
Febrile Neutropenia	51%	32%	25%	28%	Unknown
Thrombocytopenia	43%	40%	35%	24%	Unknown
Neutropenia	33%	32%	20%	26%	Unknown
Anemia	25%	34%	27%	16%	Unknown
30-day mortality	5.9%	9%	8%	6.6%	26%
60-day mortality	15.7%	19.7%	23%	16.2%	Unknown

^a Number of subjects smaller than in

Table 9, reflecting subjects who actually received treatment.

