6.1 Randomization

Eligible subjects will be randomly assigned to study treatment. Treatment assignments for the individual subjects will be determined through a computer generated randomization scheme and accessed through an interactive response system. Instructions for access and use of the interactive response system for randomization will be provided to participating study centers separately. Randomization will be 1:1 between SGI-110 and TC groups, and will be stratified by age (<75 or ≥75 years), ECOG performance status (0-1 or 2-3; see [Appendix 1](#) for the ECOG criteria), study center region (North America, Europe, rest of world [ROW]), and secondary AML (secondary to MDS or other antecedent hematologic disorder) or poor-risk cytogenetics (either, neither; see [Appendix 2](#)). Selection of 1 of the TCs must be made prior to the randomization of each subject. Subjects should receive study treatment as soon as possible after randomization (maximum of 1 week between randomization and treatment).

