11.7 Safety Analyses

Safety will be assessed by subject-reported and investigator-observed AEs and 30- and 60-day all-cause mortality, along with physical examination, clinical laboratory tests (hematology, chemistries), and ECGs. Safety variables will be tabulated and presented for all subjects who receive any amount of study treatment (SGI-110 or TC). Exposure to study treatment, reasons for discontinuation, deaths and causes of deaths will be tabulated. Treatment-emergent AEs (TEAEs) are defined as events that first occurred or worsened after the first dose of study drug given on Cycle 1 Day 1. TEAEs will be mapped to the appropriate System Organ Class (SOC) and Preferred Term (PT) according to the Medical Dictionary for Regulatory Activities (MedDRA). Severity of AEs will be graded using CTCAE version 4.03.

Summaries will be provided for all AEs, AEs considered related to study treatment, SAEs, and related SAEs as follows:

- By maximum severity.
- Incidence by SOC (by severity grade and overall).
- Incidence by PT (by severity grade and overall) within each SOC.

The percentage of 30- and 60-day all-cause mortality will be calculated based on each subject's date of death relative to Course 1 Day 1 (C1D1; ie, date of death minus date of C1D1) and compared between the 2 treatment groups using a Chi-square test.

Laboratory values reported by different local labs will be listed. Laboratory values will also be graded, if possible, by CTCAE in conjunction with the Harrison (18th edition) lab book normals (Longo 2011). Shift tables will display (1) shift from baseline grade to the worst grade, and (2) shift from baseline grade to the last grade.

Concomitant medication will be coded by the WHO Drug Dictionary and summarized by Therapeutic subgroup (ATC level 2) and PT, sorted alphabetically, using counts and percentages. Concomitant medications are the medications taken with a start date on or after the start of the administration of study treatment (C1D1), or those with a start date before the start of the administration of study treatment (C1D1) and a stop date on or after the start of the administration of study treatment (C1D1).

Vital signs will be summarized by visit using proportion of subjects with each vital sign being too high or too low according to conventionally accepted vital sign normal ranges. ECG data will be listed.

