### **5.3 Safety Analysis Set**

The Safety Analysis Set will include data from all subjects randomly assigned to study treatment who receive any amount of study treatment or any component of a multi-dose study treatment regimen. All data will be included and no subjects excluded because of protocol violations. For safety data analysis, subjects will be included in the treatment group according to the treatment they actually receive. If more than one type of study treatment was given for any subject during the study, the initial treatment received by the subject will be used to determine which treatment group and which specific TC treatment the subject belongs to.

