## 7.4 Safety Variables and Analyses

All safety analyses will be performed using the Safety Analysis Set which includes data from all subjects who receive any amount of study treatment (guadecitabine or TC; see [Section 5.3](#)).

Safety is assessed by subject-reported and investigator-observed AEs, and 30-day and 60 day all-cause mortality, along with concomitant medications, physical examination, clinical laboratory tests (hematology, serum chemistry, and urinalysis), vital signs, ECOG performance status, and ECGs. Safety is also assessed by exposure to guadecitabine or TC, reasons for discontinuation, deaths and causes of deaths.

All safety data collected during the study will be included in the study database. All safety data collected during the study will be used for generation of safety summary tables, with the exception of AEs and medications. The AE and medication summary tables will only include treatment-emergent AEs and concomitant medications as defined in [Sections 7.4.2 and 7.4.4](#).

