### 7.4.1 Study Treatment Exposure

Cycle 1 Day 1 is defined as the first day of study treatment after randomization; cycle days are counted sequentially thereafter. Cycle 2 Day 1 is the first day of Cycle 2 regardless of treatment delays. The designated cycle duration is 28 days but any cycle could be prolonged to >28 days to allow blood count recovery if deemed clinically necessary. This convention for determining the start and stop dates for cycles is maintained until treatment is permanently discontinued. For easy presentation, Cycle x Day y is often abbreviated as CxDy in this document and statistical outputs.

Frequency counts and percentages of dose cycles received, dose cycles delayed, and dose reduced cycles will be summarized by treatment group. Summary statistics of number of cycles received, as well as percentages of intended dose received, will also be provided by treatment group. Dose delayed cycles are identified by the study site and entered into the electronic data capture (EDC) system. A dose reduced cycle is defined as a cycle in which the dose was reduced by 20% or more, compared with the planned Cycle 1 dose. Percentage of intended dose is equal to actual total dose divided by planned total dose through the last treatment cycle. Both completed or partially completed dose cycles are counted in these summaries.

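### 30- and 60-day mortality is planned only in dosed subjects, from first dose, so deaths in never-dosed subjects are left out, possibly unequally by arm, with no estimate by randomized arm alongside

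*SAP*

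**What the plan says.** Mortality at 30 and 60 days is a listed secondary endpoint (Protocol 4.3.2, SAP 3.2.2).

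- **Clock.** SAP 7.4.3 uses "date of death relative to C1D1 (ie, date of death minus date of C1D1". Protocol 11.7 agrees: "date of death relative to Course 1 Day 1 (C1D1; ie, date of death minus date of C1D1". SAP 7.4.1 adds that "Cycle 1 Day 1 is defined as the first day of study treatment after randomization", so a subject who is never dosed has no Day 1.
- **Population.** SAP 7.4: "All safety analyses will be performed using the Safety Analysis Set which includes data from all subjects who receive any amount of study treatment". Within that set, SAP 5.3 states that "subjects will be included in the treatment group according to the treatment they actually receive".
- **Timing and blinding.** Protocol 6.1 allows a "maximum of 1 week between randomization and treatment". Under Protocol 6.2 and SAP 3.1, sponsor, investigators and subjects all know the assignment.
- **Comparison.** Protocol 11.7 has the percentages "compared between the 2 treatment groups using a Chi-square test". SAP 7.4.3 names no test.
- **What is planned from randomization.** Overall survival is analysed in all randomized subjects from the randomization date (SAP 5.2, 7.3.3), with Kaplan-Meier curves, quartiles and a 12-month rate. If hazards are not proportional, SAP 7.3.13 adds survival at 6, 12, 18 and 24 months and interval hazard ratios starting with months 0 to 6. SAP 7.1 tabulates numbers randomized and treated. No 30- or 60-day estimate by randomized arm is specified.

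**The concern.** The arms are compared on a set of subjects defined after randomization, with the assignment known. A subject who dies, deteriorates or withdraws between randomization and first dose is in neither numerator nor denominator. If that happens more often in one arm, and to subjects whose mortality differs from that of dosed subjects, the comparison no longer has the protection of randomization.

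The SAP handles its co-primary endpoints the other way round. For CR and OS the all-randomized analysis is primary, and the as-treated analysis, which drops undosed subjects, is a sensitivity analysis (SAP 7.3.2, 7.3.3). For early mortality the dosed-only version is the only one.

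The endpoint carries weight in the sponsor's own argument. Protocol 4.2 lists avoiding treatment-induced early mortality among the goals of therapy. Protocol 2.1 uses 30- and 60-day mortality to argue that safety is comparable with existing drugs. Protocol 2.2.3.2 cites 60-day mortality of 19.2% against 15.7%, a gap of 3.5 points, among its reasons for choosing the regimen. Differences of a few points are thus treated as informative.

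**Working it through.** **1. The plan's own figures.** The documents give no planning value for 30- or 60-day mortality. The OS figure reproduces: 4 × (1.960 + 1.282)² / [ln(7/9)]² gives 666 deaths against 670 stated, and power at 670 is 90.2% against 90%. OS runs from randomization in all randomized subjects, so this point does not touch it.

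**2. Never-dosed rates.** None are given for this trial. The only indication is in Protocol 2.1, for a cited open-label decitabine trial. Table 9 has 242 (decitabine) and 215 (low-dose cytarabine). Table 10 has 238 and 208, with a footnote explaining the smaller numbers as "reflecting subjects who actually received treatment". I take the Table 9 counts as those assigned.

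- Decitabine: (242 − 238)/242 = 4/242 = 1.7%
- Low-dose cytarabine: (215 − 208)/215 = 7/215 = 3.3%
- Fisher exact p = 0.36

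The other two comparator columns show no drop: azacitidine 241 in both tables, and the second low-dose cytarabine column 102 in both.

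**3. Effect on the comparison.** Let N be subjects per arm, D true deaths by Day 60 among all randomized, u the never-dosed fraction, and q the share of never-dosed subjects dead by Day 60. The dosed-only rate is

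r = (D − q·u·N) / (N − u·N).

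Take N = 400 (SAP 4.0) and D = 80, that is, 20% in both arms. The 20% is an assumption; Protocol 1.2 gives 18% to 23% for cited trials. Never-dosed subjects are then 400 × 4/242 = 6.6 in arm A and 400 × 7/215 = 13.0 in arm B. The labels are arbitrary, because the documents do not say which arm would lose more.

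| q (assumed) | Arm A | Arm B | A − B |
|---|---|---|---|
| 0% | 80/393.4 = 20.3% | 80/387.0 = 20.7% | −0.3 points |
| 20% | 78.7/393.4 = 20.0% | 77.4/387.0 = 20.0% | 0 |
| 50% | 76.7/393.4 = 19.5% | 73.5/387.0 = 19.0% | 0.5 points |
| 100% | 73.4/393.4 = 18.7% | 67.0/387.0 = 17.3% | 1.35 points |

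The all-randomized rate is 20% against 20% in every row. With q = 100%, a true rate of 15.7% gives 1.42 points and 23% gives 1.30, so the choice of 20% matters little. A harsher assumption of 1% against 5% never dosed, all dying, gives 76/396 = 19.2% against 60/380 = 15.8%, or 3.4 points. If u and q are equal in the two arms, the distortion is nil.

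**4. Scale.** The 95% CI half-width for 400 against 400 at 20% is 1.96 × √(2 × 0.2 × 0.8/400) = 5.5 points.

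**5. Deaths during the wait.** At a constant hazard matching the planning medians, deaths before dosing are 400 × [1 − exp(−ln 2 × d / (median × 30.4375))]. If every subject waited d = 7 days, that is 9.0 (7-month median) or 7.0 (9-month median) per 400. At 3 days it is 3.9 or 3.0. These subjects are part of the never-dosed group and must not be added to it. Under a constant hazard common to all subjects, the 30-day risk from first dose equals the 30-day risk from randomization, so moving the origin does not by itself bias the rate. Distortion needs selective non-dosing or a hazard that varies over the wait.

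**The case against.** The strongest reply is that this is the usual safety convention. The measure sits under safety in both documents and outside the testing hierarchy of SAP 7.3.7. The goal in Protocol 4.2 concerns deaths caused by treatment, which a death before dosing cannot be. No death is lost to the trial, since co-primary OS counts all of them from randomization. SAP 7.3.3 also gives Kaplan-Meier curves and quartiles, and the never-dosed count follows by subtraction from the disposition table. Protocol 6.1 asks for dosing as soon as possible and Protocol 9.5.2 for randomization close to the first dose, so the wait should usually be under a week.

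Much of this stands. The dosed-only analysis is legitimate and should stay, and the trial's main conclusions are not at risk. It does not close the gap. With an exponential 7-month median, the first quartile falls at 7 × ln(4/3)/ln 2 = 2.9 months, beyond Day 60. The fixed-time estimates begin at 6 months and are conditional. A listed endpoint that the protocol compares between arms still has no estimate that respects randomization.

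A reader might go further and infer that deaths in this trial do drop out unequally, or that the arm with more never-dosed subjects must show lower early mortality. The documents support neither. They give no rates by arm for this trial, and the 4/242 against 7/215 comparison is compatible with chance. The direction depends on whether never-dosed subjects die faster than dosed ones: in the table the effect vanishes at q = 20% and reverses below it.

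**Conclusion.** The point holds as a gap in the planned reporting. Early mortality is estimated only in dosed subjects, from first dose and by treatment received. Deaths in never-dosed subjects are left out and could be left out unequally.

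At the never-dosed rates of the one cited trial that shows a drop, the distortion of the 60-day comparison is 0 to about 1.35 points as q runs from 20% to 100%. That is small beside a CI half-width of about 5.5 points. It reaches 3.4 points only under the harsher assumption of 1% against 5% never dosed with all of them dying. These figures rest on assumed never-dosed rates, an assumed true rate of 20% in both arms, and assumed mortality among the never-dosed. Neither the presence of a bias nor its direction can be established from the documents. The effect is confined to this secondary safety endpoint.

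**What to change.** In SAP 7.4.3:

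- Add 30- and 60-day all-cause mortality from the date of randomization in the Efficacy Analysis Set, by randomized arm, with the between-arm difference and its 95% CI. Take Kaplan-Meier estimates from the OS data, so that early losses are censored. SAP 7.4.3 now scores losses to follow-up as alive, and carrying that rule over to never-dosed subjects who withdraw could understate their mortality.
- Keep the C1D1-based Safety Analysis Set figures, labelled as the on-treatment version.
- Tabulate by randomized arm the number never dosed and the number of deaths before C1D1.

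The cost is SAP wording and one extra table from dates already held for OS. Conduct, data collection and alpha do not change. The downside is that the added table includes deaths that the drug cannot have caused, which is why the on-treatment version stays beside it. Censoring also assumes that early losses are not informative about survival. Protocol 5.4.2 already asks for survival information on withdrawn subjects, which limits how far that assumption is relied on.

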Table 4 shows that safety was generally comparable between 60 and 90 mg/m² SGI-110 doses in the Phase 2 study. Higher Grade ≥ 3 neutropenia was observed at the 90 mg/m² dose.

Table 4: 60 vs 90 mg/m² (Daily \times 5 Regimen): Previously Untreated Elderly Subjects with AML (Phase 2): Grade ≥ 3 AEs with Incidence $\geq 15\%$, Regardless of Relationship to SGI-110

Adverse Event (AE) (MedDRA Preferred Term)	Number (%) of Subjects		
	60 mg/m ² (N=24)	90 mg/m ² (N=27)	Total (N=51)
Any Grade ≥ 3 AE	22 (92)	25 (93)	47 (92)
Febrile neutropenia	13 (54)	13 (48)	26 (51)
Thrombocytopenia	12 (50)	10 (37)	22 (43)
Neutropenia	5 (21)	12 (44)	17 (33)
Anemia	7 (29)	6 (22)	13 (25)
Leukopenia	5 (21)	7 (26)	12 (24)
Pneumonia	5 (21)	5 (19)	10 (20)

Source: Table EOP2 AE_G3 6.3 (2 May 2014)

Treatment-related mortality in elderly patients on intensive induction remission therapy is usually high (on the order of 25% and up to 50%). Table 5 presents all-cause mortality in elderly subjects with AML from the Phase 2 study after SGI-110 treatment. The 30- and 60-day all-cause mortality rates were low (5.9% and 15.7%, respectively) when compared with intensive induction even though most intensive induction studies in the elderly reported only treatment-induced mortality rather than all-cause mortality (Estey 2007).

Table 5: 60 vs 90 mg/m² (Daily \times 5 Regimen): All-Cause Mortality in Previously Untreated Elderly Subjects with AML Treated with SGI-110 (Phase 2)

Dose	N	Number (%) of Subjects	
		30-day Mortality	60-day Mortality
All Previously Untreated AML	51	3 (5.9)	8 (15.7)
60 mg/m ²	24	2 (8.3)	4 (16.7)
90 mg/m ²	27	1 (3.7)	4 (14.8)

Source: EOP2_DEATH (26 Apr 2014 database cut-off date)

LINE-1 DNA methylation data before and after treatment were available in 49 subjects (96%). Average maximum LINE-1 demethylation was similar for the 60 mg/m² and 90 mg/m² dose groups (-19% for 60 mg/m² and -21% for 90 mg/m²).

Based on a trend of improvement in response rate in relapsed/refractory AML with a 10-day regimen of SGI-110 (Section 1.3.2.2.2), a new cohort of 52 treatment-naïve elderly subjects with AML was treated with the 10-day regimen. Emerging preliminary data (study is still ongoing) suggest that this 10-day regimen in treatment-naïve elderly subjects is unlikely to be associated

with a significantly higher response rate than the Daily×5 regimen in this population and may be associated with higher toxicity.

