## 4.0 SAMPLE SIZE

By trial design, the overall (2-sided) alpha level of 0.05 is split between the co-primary endpoints of CR (0.04) and OS (0.01). A formal interim analysis will be performed only for OS using a group sequential boundary preserving an overall (2-sided) 0.01 alpha level. The sample size calculation for the primary analysis of CR is based on testing at the 0.04 nominal alpha level. If statistical significance is achieved for CR, hierarchically, the final analysis of OS will be conducted to preserve an overall 2-sided 0.05 alpha level, accounting for alpha spent at the interim analysis of OS, as described in Section 11.6.7 and Section 11.9 of the study protocol (see Section 7.3.7 and 7.6). The sample size calculation for OS will be shown for the setting of a 2-sided 0.05 alpha level.

Assuming a CR rate of approximately 0.20 ([Kantarjian et al 2012](#); [Fenaux et al 2010](#); [Burnett et al 2007](#)) for subjects treated in the TC group (all TC therapies combined) and assuming an increase in CR rate to 0.30 or higher can be achieved by treating subjects with guadecitabine,

800 subjects (400 per treatment group) will provide approximately 89% power to detect the overall difference of 0.10 when using a 2-sided Cochran Mantel-Haenszel test having 2-sided alpha level of 0.04. For the purpose of this sample size calculation, the constant CR rates of 0.20 and 0.30 for the TC and guadecitabine groups, respectively, are assumed for each stratum.

For survival, an analysis at 670 death events will provide 90% power to detect a HR of approximately 0.78 (a difference in median survival of 7 months in the TC group versus 9 months in the guadecitabine group), when using a 2-sided stratified log-rank test at an 0.05 alpha level. Accrual is expected to be uniform over a 21 month enrollment period, with an additional follow-up of 12 months. Hence, the assessment of survival needs approximately the same sample size of 800 subjects. Primary response and survival analyses will be performed after 670 death events have occurred. For the purpose of this sample size calculation, a constant HR of approximately 0.78 was assumed for all strata defined by the stratification factors.

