#### 7.3.5 Number of Days Alive and Out of the Hospital

The date of each hospital admission and discharge will be collected for each subject for a minimum 6 months (and until termination of study treatment if the study treatment lasts for more than 6 months), unless the subject dies or withdraws consent prior. The duration of each hospital stay in days (regardless of the reason for hospitalization) is calculated as:

$$\text{Duration} = \text{date of discharge} - \text{date of admission}$$

For a subject who is admitted and discharged on the same day the duration of hospital stay will be 0. The total duration of all hospital stays in the first 6 months is the sum of all individual

durations of hospital stays occurred between C1D1 and Day 180. For ease of calculation, one month is defined as 30 days for analyses conducted in this study. The NDAOH within the first 6 month period is calculated as:

$$\text{NDAOH} = 180 - \text{total duration of all hospital stays} - \text{number of death days before Day 180}$$

The number of death days before Day 180 = (date of Day 180 - date of death, if death occurs before Day 180). For subjects who die on or after Day 180 the number of death days before Day 180 will be set to 0. For subjects who are lost to follow-up within 6 months (expected to be a very small number), the NDAOH will be calculated conservatively assuming that the subject would have died the day after the last contact day.

The NDAOH will be summarized by treatment group and compared between the 2 treatment groups using an analysis of variance model at an alpha level of 0.05 or 0.01 as appropriate, if the CRc test result is significant at that required level (see Section 7.3.7). The variables used for stratification at randomization will be included in the analysis of variance model as fixed factors.

In addition, to utilize the information on hospital stays beyond 6 months, the NDAOH will also be calculated in a similar way to 6 months or the date of treatment discontinuation (whichever occurs later) and summarized as a per patient-year rate for each treatment group.

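### Counting subjects lost before Day 30 or Day 60 as alive can only understate early mortality; the effect is small if loss is rare, and a Kaplan-Meier estimate with a worst-case count would address it

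*SAP*

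**What the plan says.** Early all-cause mortality is a listed secondary endpoint (Protocol 4.3.2, SAP 3.2.2) and is analysed with safety. SAP 7.4 fixes the population: "All safety analyses will be performed using the Safety Analysis Set which includes data from all subjects who receive any amount of study treatment". SAP 7.4.3 counts days from C1D1 to death and handles loss with one rule: "subjects who were lost-to-follow-up within 30- or 60-days from C1D1 (assumed to be a very small number, if any) will be considered alive". The stated reason is "To avoid using a different denominator for calculation of the percentage of 30- and 60-day mortality".

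Three other places bear on this:

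- **SAP 7.3.5 (days alive and out of hospital, NDAOH).** A subject lost within 6 months is handled the opposite way, "assuming that the subject would have died the day after the last contact day".
- **SAP 7.3.3 (OS).** A subject without a death is censored at the last date known alive.
- **Protocol 11.7.** The 30- and 60-day percentages are to be "compared between the 2 treatment groups using a Chi-square test". SAP 7.4.3 gives percentages, causes of death and relationship to treatment, but no comparison.

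Neither document plans a sensitivity analysis for the early-mortality rates.

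**The concern.** For a safety rate, imputing survival is the anti-conservative direction. Observed deaths can never exceed actual deaths, and the denominator is fixed, so the error runs one way within each arm. Between arms it can go either way: if one arm loses more subjects, its early mortality looks relatively better. The trial is open-label, so unequal loss is possible.

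The stated reason does not require the rule. A Kaplan-Meier estimate from C1D1 starts from the same treated subjects at both time points and does not assume that a lost subject survived.

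Early mortality also carries weight in the sponsor's reasoning. Protocol 4.2 names avoiding treatment-induced early mortality as a goal of therapy. Protocol 2.2.3.2 cites 60-day mortality of 19.2% against 15.7% among its reasons for choosing between regimens.

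**Working it through.** The plan states no rate or power for this analysis, so there is no planned figure to reproduce. The question is how far the crude percentage falls below the true risk.

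**Inputs**

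- True 60-day risk *m*: 15.7% (Phase 2, 8/51, Protocol Table 5), 20% as a round middle value, and 23% as the top of Protocol Table 10, whose 60-day figures are 15.7%, 19.7%, 23% and 16.2%.
- Treated per arm: 400, the planned arm size in SAP 4.0, assuming all are treated.
- Loss by Day 60, *L*: not given beyond "assumed to be a very small number, if any". Assumed 0.5% to 5%, where *L* is the chance of loss by Day 60 in the absence of death.

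**Model.** Constant hazards over 60 days, with the same death hazard after loss as before. Cumulative hazards are H = −ln(1 − m) and C = −ln(1 − L).

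Crude rate = H/(H + C) × [1 − (1 − m)(1 − L)]

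Example, m = 15.7% and L = 2%: H = 0.1708, C = 0.0202, so the crude rate is 0.1708/0.1910 × (1 − 0.843 × 0.98) = 0.894 × 0.1739 = 15.55%. The shortfall is 0.15 points. Kaplan-Meier returns 15.70%.

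| True 60-day risk | L = 0.5% | L = 1% | L = 2% | L = 5% |
|---|---|---|---|---|
| 15.7%: crude (shortfall) | 15.66 (0.04) | 15.62 (0.08) | 15.55 (0.15) | 15.32 (0.38) |
| 20%: crude (shortfall) | 19.95 (0.05) | 19.90 (0.10) | 19.81 (0.19) | 19.51 (0.49) |
| 23%: crude (shortfall) | 22.94 (0.06) | 22.89 (0.11) | 22.78 (0.22) | 22.45 (0.55) |

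At m = 15.7%, these loss rates mean about 1.8, 3.7, 7.4 and 18.4 subjects lost per arm of 400.

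**Informative loss (m = 15.7% among those followed).** If lost subjects die at three times the hazard, the crude figure is low by 0.10 to 1.03 points across L = 0.5% to 5%, and Kaplan-Meier is also low, by 0.06 to 0.65 points. If no lost subject dies in the window, the crude figure is exact and Kaplan-Meier is slightly high (by 0.15 points at L = 2%).

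**Worked counts.** Take 400 treated, 32 deaths by Day 30 and 31 more by Day 60, with *x* subjects lost at Day 30.

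- Crude = 63/400 = 15.75% for every *x*.
- Kaplan-Meier = 1 − (1 − 32/400) × (1 − 31/(368 − x)).
- Worst case = (63 + x)/400.

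| Lost (x) | Crude | Kaplan-Meier | All lost counted dead |
|---|---|---|---|
| 0 | 15.75% | 15.75% | 15.75% |
| 2 | 15.75% | 15.79% | 16.25% |
| 4 | 15.75% | 15.84% | 16.75% |
| 8 | 15.75% | 15.92% | 17.75% |
| 20 | 15.75% | 16.20% | 20.75% |

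With equal known deaths and 0 lost in one arm against 8 in the other, the between-arm difference is 0 by the SAP rule, 15.92 − 15.75 = 0.17 points by Kaplan-Meier, and 17.75 − 15.75 = 2.0 points in the worst case.

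**Against sampling error.** With 400 per arm, the standard error of a 15.7% rate is √(0.157 × 0.843/400) = 1.8 points. The 95% half-width for a difference between 15.7% and 20% is 1.96 × √(0.157 × 0.843/400 + 0.20 × 0.80/400) = 5.3 points.

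**The case against.** The strongest reply is that the effect is immaterial. The SAP expects hardly any loss, and the schedule supports that: visits on every treatment day and on Days 8, 15 and 22 of Cycles 1 and 2, monthly visits up to 6 months for subjects who stop before Cycle 6, and survival information sought even after withdrawal (Protocol 9.5.3, 9.5.6, 5.4.2). The analysis waits for 670 deaths, so a subject out of contact at Day 60 but traced later is not missing. Even 0.5 points is well inside sampling error. This stands, and it is why the point is minor. It does not remove the one-way direction, and it rests on an expectation that the SAP does not plan to check for this endpoint.

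A second reply is that the OS curves already show Days 30 and 60 with censoring. That is partly so, but they run from randomization and include untreated subjects, so they do not estimate the treated-set rate from C1D1.

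A third is that crude percentages are what the protocol specifies and match the Phase 2 tables. True, and a reason to keep them. But Protocol 11.7 states no rule for lost subjects; that comes only from the SAP.

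Some stronger readings are tempting but not supported:

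- *Kaplan-Meier removes the bias.* It replaces survival after loss with non-informative loss. If loss signals imminent death, it is low too.
- *The SAP contradicts itself because NDAOH counts the same subject as dead.* The rules serve different endpoints, and SAP 7.7 allows specified exceptions to its general missing-data rule. The contrast is worth noting, but it is not an error.
- *Early mortality is the main safety comparison.* The documents list it as one of several secondary endpoints, outside the alpha-controlled sequence.

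**Conclusion.** The point holds as a minor one. The rule in SAP 7.4.3 can only leave early mortality at or below its true value, by more where loss is greater, and nothing planned offsets it. Under non-informative loss with a true 60-day risk of 15.7% to 20%, the shortfall is about 0.04 to 0.2 points at 0.5% to 2% loss and 0.4 to 0.5 points at 5%; at the 23% top of Protocol Table 10 it reaches 0.22 and 0.55 points at 2% and 5%. The loss rates, the constant hazards and the 400 treated per arm are assumptions. With no loss, the crude and Kaplan-Meier figures coincide.

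A reader might infer that the rule would conceal a meaningful excess of early deaths. The documents do not support that: they give no loss rate, they expect almost none, and a gap of clinical size would need substantial or clearly unequal loss. No co-primary or alpha-controlled conclusion changes.

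The missing between-arm comparison is a separate protocol-to-SAP discrepancy and stands whatever the loss rate.

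**What to change.** In SAP 7.4.3:

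1. Estimate 30- and 60-day mortality as 1 minus Kaplan-Meier from C1D1 in the Safety Analysis Set, censoring at the last date known alive. Give the between-arm difference with a 95% CI from Greenwood standard errors, which SAP 7.3.13 already uses.
2. Keep the crude counts and percentages, with the protocol's Chi-square comparison, or state why it was dropped.
3. Report, by arm, the number with unknown vital status at Day 30 and Day 60. Include withdrawals of consent, which Protocol 5.4.2 lists separately from loss to follow-up and the present rule does not mention.
4. Add a worst-case count treating those subjects as dead, because Kaplan-Meier relies on non-informative loss.

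The cost is a little extra programming and one or two more table rows. The survival data and methods are already in the plan.
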